6.6.2 Primary Effectiveness Endpoint

The primary effectiveness endpoint is defined as the mean absolute relative difference, estimated from all paired measurements from the Eversense® 180 CGM System and reference measurements up to 180 days after Sensor insertion.

For each participant, the mean absolute relative difference is

$$\text{Mean ARD} = \left(\sum_{i=1}^n \frac{|glucose(\text{sensor})_i - glucose(\text{reference})_i|}{glucose(\text{reference})_i} \right) / n \times 100\%$$

where n is the total number of pairs of the Eversense® 180 CGM System and reference measurements during the evaluation period.

Only descriptive analysis will be carried out. No hypothesis will be tested.

6.6.3 Secondary Effectiveness Endpoints

In each of the following endpoints, the subscript "i" identifies each pair of the Eversense® 180 CGM System and reference measurements during the evaluation period for each participant and n is the total number of such pairs.

Statistical Analysis Plan		Page 17 of 28
Sponsor Senseonics, Incorporated	Study PROMISE Study: A Prospective, Multicenter Evaluation of Accuracy and Safety of an Implantable Continuous Glucose Sensor Lasting up to 180 Days	Version 3.0

Mean absolute difference

$$Mean\ AD = \left(\sum_{i=1}^n |glucose(sensor)_i - glucose(reference)_i| \right) / n \times 100\%$$

Mean relative difference

$$Mean\ RD = \left(\sum_{i=1}^n \frac{glucose(sensor)_i - glucose(reference)_i}{glucose(reference)_i} \right) / n \times 100\%$$

Median absolute relative difference

$$Median\ ARD = median \left(\frac{|glucose(sensor)_i - glucose(reference)_i|}{glucose(reference)_i} \right) \times 100\%$$

for i = 1, 2, ..., n.

Median absolute difference

$$Median\ AD = median(|glucose(sensor)_i - glucose(reference)_i|) \times 100\%$$

Median relative difference

$$Median\ RD = median \left(\frac{glucose(sensor)_i - glucose(reference)_i}{glucose(reference)_i} \right) \times 100\%$$

Agreement between the Sensor and the reference measurements will be assessed by examining

$$\left(\frac{|glucose(sensor)_i - glucose(reference)_i|}{glucose(reference)_i} \right) \times 100\%$$

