11.3.2.3.1 MEAN ABSOLUTE DIFFERENCE (MAD) BETWEEN SENSOR AND REFERENCE MEASUREMENTS

$$MAD = \left(\sum |(Glucose)_{\text{SENSOR}} - (Glucose)_{\text{REFERENCE}}| \right) / n$$

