11.3.2.3.4 MEDIAN ABSOLUTE DIFFERENCE BETWEEN SENSOR AND REFERENCE MEASUREMENTS

$$\text{Median AD} = \text{Median} (|(Glucose)_{\text{SENSOR}} - (Glucose)_{\text{REFERENCE}}|_i), i = 1, 2, \dots, n$$

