11.3.2.3.6 SYSTEM AGREEMENT WITH REFERENCE

The Agreement of the CGM System to reference measurements will be assessed by looking at the differences ($\frac{|(\text{Glucose})_{\text{SENSOR}} - (\text{Glucose})_{\text{REFERENCE}}|}{(\text{Glucose})_{\text{REFERENCE}}}$) $\times 100\%$ in intervals of [0 – 15%], [0 – 20%], [0-30%], and [0-40%]. For readings less than or equal to 80 mg/dL, the absolute difference in mg/dL between the two glucose results will be calculated. For values greater than 80 mg/dL, the absolute percent difference (%) from the reference values will be calculated.

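### The SAP's formulas for mean and median absolute difference carry a stray × 100% on a quantity in mg/dL, in conflict with the protocol and with the SAP's own table footnotes.

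*SAP*

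**What the plan says.** The SAP lists its accuracy measures other than MARD under "6.6.3 Secondary Effectiveness Endpoints". Two of them are absolute differences:

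- Mean AD ends in "glucose(sensor)_i - glucose(reference)_i| \right) / n \times 100", followed by a percent sign.
- Median AD is "median(|glucose(sensor)_i - glucose(reference)_i|) \times 100", also followed by a percent sign.

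The protocol defines the same two measures without that factor:

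- Section 11.3.2.3.1: "MAD = \left(\sum |(Glucose)_{\text{SENSOR}} - (Glucose)_{\text{REFERENCE}}| \right) / n".
- Section 11.3.2.3.4: "Median AD} = \text{Median} (|(Glucose)_{\text{SENSOR}} - (Glucose)_{\text{REFERENCE}}|_i), i = 1, 2, \dots, n".

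On units, Protocol section 11.3.2.3.6 says that for readings at or below 80 mg/dL "the absolute difference in mg/dL between the two glucose results will be calculated", with percent difference used above that level. The footnotes to SAP tables A.7.1 and A.7.2 say that at or below 80 mg/dL the entries are mg/dL differences in place of percentages.

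**The concern.** Multiplying by 100% turns a dimensionless ratio into a percentage. It suits the relative measures, where each difference is divided by the reference reading. An absolute difference is not divided by anything, so it keeps the unit of the glucose readings, mg/dL, and a percent sign on it has no meaning.

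The two formulas are endpoint definitions, not background text. A programmer who applies one convention to every line of section 6.6.3 would produce two secondary endpoints on the wrong scale and with the wrong unit. Other parts of the SAP give only partial protection. Section 6.6.4 uses the means and medians of absolute difference again without naming a unit. In tables A.7.1 and A.7.2 the difference columns are headed in percent, and only a footnote signals mg/dL for the low-glucose rows.

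**Working it through.** The plan states no numerical value for absolute difference, and no sample size or threshold depends on it, so there is no figure to reproduce. The check has three parts.

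**1. Units.** Glucose readings are in mg/dL (SAP section 3.2.1 gives the reference range as 40-400 mg/dL).

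| Measure | Divided by reference? | Unit before scaling | SAP factor | Protocol factor |
|---|---|---|---|---|
| Mean ARD (MARD) | yes | none | × 100% | × 100% |
| Mean RD | yes | none | × 100% | × 100% |
| Median ARD | yes | none | × 100% | × 100% |
| Median RD | yes | none | × 100% | × 100% |
| Mean AD | no | mg/dL | × 100% | no factor |
| Median AD | no | mg/dL | × 100% | no factor |

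The documents differ only in the last two rows, and those are the rows where the factor does not belong.

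**2. What the factor means in the SAP.** The relative measures in section 6.6.3 need it to mean: multiply by 100 and report in percent. Section 6.6.5 points the same way, since Paired ARD is written with × 100% and PCV with a leading 100 × for the same scaling.

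**3. A worked example.** These four pairs are assumed for illustration and do not come from the documents: reference 60, 100, 200, 350 mg/dL; sensor 70, 90, 215, 320 mg/dL.

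- Absolute differences: 10, 10, 15, 30 mg/dL.
- Protocol Mean AD = (10 + 10 + 15 + 30) / 4 = 65 / 4 = 16.25 mg/dL.
- Protocol Median AD = (10 + 15) / 2 = 12.5 mg/dL.
- SAP formulas under the convention in step 2: 16.25 × 100 = 1625, labelled %; 12.5 × 100 = 1250, labelled %.
- Ratio of SAP to protocol: 1625 / 16.25 = 100 and 1250 / 12.5 = 100. The ratio is 100 whatever the data.
- Relative measures on the same pairs: 10/60, 10/100, 15/200 and 30/350 give a mean ARD of 10.7% and a median ARD of 9.3%. Here the factor is right.

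By the same arithmetic, an assumed mean error of 15 mg/dL would be reported as 15 × 100 = 1500%.

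**The case against.** Four arguments go the other way.

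**100% is algebraically 1.** Read literally, the formulas leave the value unchanged in mg/dL. This stands as algebra. A reader might infer that both endpoints are bound to come out 100 times too large; the documents do not support that, because the inflation arises only if the factor is programmed as in the neighbouring formulas. Even on the literal reading, though, a percent sign is wrong on a mg/dL quantity.

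**The intended unit can be recovered.** A reader might also infer that the SAP formula overrides the protocol in programming. No text says so: the SAP introduction asks that it be read together with the clinical investigation plan, which has both formulas right. That limits the risk, but it leaves two documents in conflict over two named measures.

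**The low-glucose rows are protected.** It is tempting to say that accuracy in hypoglycemia is where the harm would fall, because mg/dL differences replace percentages there. But the footnotes to A.7.1 and A.7.2 state mg/dL for exactly those rows. The sample tables available for review have no separate Mean AD or Median AD column; part of the appendix was not available, so other tables could not be checked.

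**Little depends on these figures.** All analyses are descriptive, no acceptance limit for absolute difference is given, and Protocol section 11.3.2.3 classes these measures as exploratory although the SAP calls them secondary. A mean difference above 1000% would be conspicuous beside an ARD near 10%. This bears on how serious the slip is, not on whether the formulas are right.

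A difference between document versions does not explain the conflict. The SAP was written to Protocol Version 7 and the protocol reviewed is Version 09, but the log entries for 08 and 09 concern the extension to one year and its visits, and mention no change to these formulas.

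**Conclusion.** The point holds. The Mean AD and Median AD formulas in SAP section 6.6.3 are wrong as written, and they conflict with Protocol sections 11.3.2.3.1 and 11.3.2.3.4 and with the SAP's own footnotes. The likeliest cause is that the ending of the relative formulas was carried onto every line.

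The possible error is a factor of exactly 100 with a percent label in place of mg/dL, on two secondary endpoints. It is conditional on the formulas being programmed by the convention that the relative measures require. MARD, Mean RD, Median ARD, Median RD and the agreement expression are unaffected. No hypothesis test or design quantity changes, and no data would be lost if the slip were found late. It should be corrected, but it does not threaten the study's main result.

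**What to change.** In SAP section 6.6.3, delete × 100% from the Mean AD and Median AD formulas and state the unit of both as mg/dL, so that they match Protocol sections 11.3.2.3.1 and 11.3.2.3.4. Leave the relative measures and the agreement expression as they are. Naming mg/dL for absolute difference in section 6.6.4 would close the remaining gap.

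The cost is one wording correction, with no effect on design, data collection or sample size. SAP section 7 provides for changes to be made in an amended SAP before analysis when possible, so the correction should be recorded there and not made silently in the programs.

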6.6.4 Other Effectiveness Endpoints

The means and medians of absolute relative difference, absolute difference and relative difference when the reference measurements (Yellow Springs Instrument analyzer) will be presented.

The agreement between the Sensor and the reference measurements at different ranges of reference measurements and of Sensor measurements will also be presented.

Statistical Analysis Plan		Page 18 of 28
Sponsor Senseonics, Incorporated	Study PROMISE Study: A Prospective, Multicenter Evaluation of Accuracy and Safety of an Implantable Continuous Glucose Sensor Lasting up to 180 Days	Version 3.0

Concurrence of the Sensor and the reference standard (Yellow Springs Instrument analyzer) will be presented as Tables. Performance of the Eversense® 180 CGM System over the study period will be assessed by visit.

6.6.5 Device Precision

The means of the following two measures will be tabulated.

Paired absolute relative difference

$$\text{Paired ARD} = \left(\sum_{i=1}^n \frac{|glucose(\text{sensor 1})_i - glucose(\text{sensor 2})_i|}{\frac{1}{2} \times (glucose(\text{sensor 1})_i + glucose(\text{sensor 2})_i)} \right) / n \times 100\%$$

Percent Coefficient of Variation

$$\text{PCV} = \sum_{i=1}^n (100 \times \frac{\text{SD of } (glucose(\text{sensor 1})_i \text{ and } glucose(\text{sensor 2})_i)}{\text{Mean of } (glucose(\text{sensor 1})_i \text{ and } glucose(\text{sensor 2})_i)}) / n$$

6.7 Poolability Analyses

All investigational sites follow the requirements of a common protocol and standardized data collection procedures and forms.

Data from different study sites will be pooled for analyzing the primary effectiveness measure. Study site effects will only be examined descriptively. Sites enrolling fewer than five participants will be combined as one group.

6.8 Safety Analyses

Adverse events (AE) will be reported for the safety analysis population. Adverse events will be tabulated with the number of events and subjects with event for each event type and overall. Rates will be reported as the number of subjects who experience at least one event during the analysis interval out of the total number of subjects with follow-up to the beginning of the analysis interval. Serious adverse events will also be tabulated.

Adverse events leading to death or study discontinuation will be provided as Listings.

Statistical Analysis Plan		Page 19 of 28
Sponsor Senseonics, Incorporated	Study PROMISE Study: A Prospective, Multicenter Evaluation of Accuracy and Safety of an Implantable Continuous Glucose Sensor Lasting up to 180 Days	Version 3.0

All device deficiencies for the Sensor and the transmitter will be reported as Tables and Listings.

6.9 Additional Analyses

Descriptive analysis will be carried out on data from all participants, and separately for each of the following groups. No hypothesis testing on the difference between groups will be carried out.

- Type 1 versus Type 2 diabetes mellitus.
- Age (18-20, 21-44, 45-65, and over 65 years)
- Baseline HbA1c level below 8% versus 8% or over
- Glucose range strata (e.g. <40, 40-60, 61-80, 81-180, 181-300, 301-350, 351-400, > 400 mg/dL) to include all samples, i.e. more frequent than 15-minute sampling

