4.3.9.2 TIMING OF BLOOD SAMPLING

Blood will be sampled approximately every 5 to 15 minutes, dependent on the value of the previous sample according to the following ranges:

- BG \geq 300 mg/dL: every 5 minutes (+/- 2 minutes) *
- BG >70 mg/dL and < 300 mg/dL: every 15 minutes (+/- 2 minutes)
- BG \leq 70 mg/dL: every 5 minutes (+/- 2 minutes)

*When > 400 mg/dL, sampling may be reduced to every 15 minutes

Blood sampling can also be reduced to every 15 minutes after the challenge is met. Additional samples may be drawn for YSI glucose analysis as needed for patient safety or to recheck a suspected erroneous value (e.g. dilute sample).

In the event of loss of IV access or loss of functional YSI and need for continued subject monitoring, glucose measurements will be made on capillary whole blood using the Subject SMBG meter as needed.

Samples missed due to loss of IV access or other interruptions will not be considered protocol deviations.

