11.3.2.4 EFFECTIVENESS MEASURE IN FULL GLUCOSE RANGE AND DIFFERENT GLYCEMIC REGIONS

Mean/median absolute relative difference, mean/median relative difference, mean/median absolute difference when reference $\text{YSI} \leq 70 \text{ mg/dL}$, and Agreement between CGM and YSI glucose will be stratified based on YSI glucose ranges. Similar stratification based on CGM glucose will also be performed. (Tables 6A-6D in APPENDIX 1).

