A.8.1 Concurrence of CGM System Readings and YSI Values within YSI Glucose Ranges (Sample Table)

YSI (mg/dL)	Number of Paired CGM-YSI (n)	Percent of Matched Pairs in Each CGM System Glucose Range for Each YSI Glucose Range								
		CGM (mg/dL)	40-60	61-80	81-120	121-160	161-200	201-250	251-300	301-350
<40										
40-60										
61-80										
81-120										
121-160										
161-200										
201-250										
251-300										
301-350										
351-400										

Statistical Analysis Plan				Page 27 of 28
Sponsor	Study			Version
Senseonics, Incorporated	PROMISE Study: A Prospective, Multicenter Evaluation of Accuracy and Safety of an Implantable Continuous Glucose Sensor Lasting up to 180 Days			3.0

YSI (mg/dL)	Number of Paired CGM-YSI (n)	Percent of Matched Pairs in Each CGM System Glucose Range for Each YSI Glucose Range								
		40-60	61-80	81-120	121-160	161-200	201-250	251-300	301-350	351-400
>400										

A.8.2 Concurrence of CGM System Readings and YSI Values within CGM System Ranges (Sample Table)

CGM (mg/dL)	Number of Paired CGM-YSI (n)	Percent of Matched Pairs in Each YSI Glucose Range for Each CGM Glucose Range YSI (mg/dL)									
		<40	40-60	61-80	81-120	121-160	161-200	201-250	251-300	301-350	351-400
40-60											
61-80											
81-120											
121-160											
161-200											
201-250											
251-300											
301-350											
351-400											

A.9 CGM System Accuracy by Visit Number (Sample Table)

Day Number	Number of Paired CGM-YSI	Mean Absolute Relative Difference (%)	Median Absolute Relative Difference (%)	Percent of CGM System Readings Within				
				Percent 15/15% of Reference	Percent 20/20% of Reference	Percent 30/30% of Reference	Percent 40/40% of Reference	Percent Greater than 40/40% of Reference
Day 1								
Day 7								
Day 14								
Day 22								

Statistical Analysis Plan		Page 28 of 28
Sponsor Senseonics, Incorporated	Study PROMISE Study: A Prospective, Multicenter Evaluation of Accuracy and Safety of an Implantable Continuous Glucose Sensor Lasting up to 180 Days	Version 3.0

Day Number	Number of Paired CGM-YSI	Mean Absolute Relative Difference (%)	Median Absolute Relative Difference (%)	Percent of CGM System Readings Within				
				Percent 15/15% of Reference	Percent 20/20% of Reference	Percent 30/30% of Reference	Percent 40/40% of Reference	Percent Greater than 40/40% of Reference
Day 30								
Day 60								
Day 90								
Day 120								
Day 150								
Day 180								

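### SAP 6.9 does not limit all-sample (5-minute) data to YSI-classified tables; in sensor-classified tables, whether a pair is included would then depend on the reference result

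*SAP*

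**What the plan says.** Protocol 4.3.9.2 makes the sampling interval "dependent on the value of the previous sample according to the following ranges": 5 minutes at ≤70 or ≥300 mg/dL, 15 minutes in between. Two relaxations are allowed. Sampling may drop to 15 minutes above 400 mg/dL, and "Blood sampling can also be reduced to every 15 minutes after the challenge is met".

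SAP 6.2 builds the per-protocol effectiveness set, which is primary for effectiveness, from reference values at 15-minute intervals. SAP 6.9 then lists glucose-range strata, from <40 to >400 mg/dL, that are "to include all samples, i.e. more frequent than 15-minute sampling".

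Both documents plan range tables by sensor value as well as by YSI. SAP 6.6.4 says agreement "at different ranges of reference measurements and of Sensor measurements will also be presented", and protocol 11.3.2.4 says "Similar stratification based on CGM glucose will also be performed". The shells are A.7.2, A.7.4 and A.8.2 in the SAP, and Tables 6B, 6D and 7B in the protocol. Neither document states any thinning or weighting of the 5-minute samples for these tables.

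**The concern.** A row defined by YSI range conditions on the variable that drives the sampling rate. The extra samples add precision there and do little else. A row defined by sensor range does not condition on that variable. Take two equal stretches of time in which the sensor shows the same low value. If YSI is also low, the stretch yields about three times as many pairs as it does if YSI is in the middle range. (The rule looks at the previous blood value, but successive values lie close together, so in effect it follows the current one.) The chance that a pair is in the row then depends on the reference result that the row is meant to report.

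A.8.2 is the most exposed table, because it gives the percentage in each YSI range for a given sensor range. The study tests no hypothesis, so its descriptive tables are the evidence. The target indication includes alerts for low and high glucose, so the low and high sensor rows will be read closely.

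**Working it through.** **1. Reproducing the plan's own counts.** Protocol 11.1.4 expects 1040 / 4400 / 1280 pairs (40–70 / 71–299 / 300–400 mg/dL), 6720 in total, on Day 1 from 160 subjects with challenge types split equally. Section 4.3 gives 8 hours (480 min) of sampling, 13 low values for a 60-minute low challenge and 16 high values for a 75-minute high challenge.

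- Low-challenge visit: 60/5 + 1 = 13 low pairs, and (480 − 60)/15 = 28 mid-range pairs.
- High-challenge visit: 75/5 + 1 = 16 high pairs, and (480 − 75)/15 = 27 mid-range pairs.
- 80 visits of each: 80 × 13 = 1040; 80 × (28 + 27) = 4400; 80 × 16 = 1280; total 6720.

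The match is exact, so the sponsor's planning assumes the 5/15-minute rule.

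**2. Over-sampling ratio, w.** On a 15-minute grid the same challenges give 60/15 + 1 = 5 low and 75/15 + 1 = 6 high values. So w = 13/5 = 2.6 and 16/6 = 2.67, with a nominal maximum of 15/5 = 3.

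**3. Overall rows.** With all samples, extremes are (1040 + 1280)/6720 = 2320/6720 = 34.5% of Day 1 pairs. On an even grid they are (80 × 5 + 80 × 6)/(880 + 4400) = 880/5280 = 16.7%.

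**4. Low and high sensor rows, clean split at the trigger.** Let f be the unconfirmed share under even sampling. The share shown is f′ = f / (f + w(1 − f)). The documents give no f, so a range is assumed:

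| f | shown, w = 3 | shown, w = 2.6 |
|---|---|---|
| 10% | 3.6% | 4.1% |
| 20% | 7.7% | 8.8% |
| 30% | 12.5% | 14.2% |
| 40% | 18.2% | 20.4% |
| 50% | 25.0% | 27.8% |

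The relative understatement is 44–64%. No planned cell splits YSI at exactly 70 (the A.8.2 columns are 61–80 and 81–120), so the planned bins need a simulation.

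**5. Planned bins, simulated.** Assumptions: unbiased sensor, 10–12% error with or without a 10–12 mg/dL floor below 100, w = 2.6–3, and two glucose mixes.

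- *YSI flat over 45–400 in time.* In the CGM 61–80 row, YSI above 80 falls from 19–25% to 10–14% (1 − 10/19 = 47%; 1 − 14/25 = 44%). In the CGM 301–350 row, YSI below 300 falls from 21–24% to 8–11% (1 − 8/21 = 62%; 1 − 11/24 = 54%).
- *The protocol's own time mix.* Low time is 80 × 60/(160 × 480) = 6.25% and high time is 80 × 75/(160 × 480) = 7.8%, taken as flat within bands. The understatement in the same cells is 36–43% and 38–46%.

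**6. Mid-range sensor rows, flat mix.** In the CGM 251–300 row, YSI above 300 rises from 26–29% to 47–55%. In the CGM 181–300 row, readings outside 15% rise from 13.6–21.5% to 16.9–27.2%.

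**7. Effect of the relaxation.** A further simulation followed the full rule, with sensor lag, autocorrelated error and an assumed MARD of about 7–13%. For a split at the trigger, unconfirmed lows were understated by 48–52% with or without the return to 15 minutes after the challenge. Unconfirmed highs were understated by 54–56%, or 43–47% with that return. Disagreement beyond 20/20% in these rows was understated by 31–52%.

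**The case against.** The strongest objection is that SAP 6.9 never names the sensor-classified tables. Its eight strata are exactly the rows of the YSI-classified A.7.1 and A.7.3. The sensor tables A.7.2 and A.7.4 have no <40 or >400 row, and A.8.2 uses finer bins. Because SAP 6.2 makes the 15-minute set primary for effectiveness, the sensor tables could be read as already resting on 15-minute data. This stands in part: a reader might take 6.9 as definitely overriding 6.2 for those tables, and the text does not go that far. But the 6.9 list is given only as an example, six of its strata are the rows of A.7.2 and A.7.4, and nothing confines it to YSI. One clarifying sentence is needed on either reading.

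A reader might also infer that the bias always favours the device. It does not: mid-range sensor rows over-count missed lows and highs, and step 6 shows that this shift can be large.

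Nor is the understatement uniformly one half. The protocol's own time mix gives 36–46% in the planned bins, and the ratio falls where sites return to 15-minute sampling after the challenge is met.

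Finally, the tables are descriptive, no predictive-value endpoint is defined, and the primary MARD is computed on 15-minute data. All of that is correct, and it limits the weight of the point without removing it.

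**Conclusion.** The point holds, conditional on 6.9 reaching the sensor-classified tables. That is its natural reading, but the SAP should confirm it. On that reading, inclusion of a pair within a sensor row depends on the reference result at a ratio of up to about 2.6–3. Unconfirmed readings in the low and high rows are understated by roughly 35–60% in relative terms. This range rests on assumed glucose mixes and sensor errors, because the documents supply neither. Mid-range sensor rows are distorted against the device, and Overall rows built on all samples are over-weighted toward the extremes.

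It would be wrong to conclude that the primary result is affected, since the 15-minute MARD set is untouched. YSI-classified rows are also nearly untouched: only 61–80 straddles the 70 mg/dL trigger and mixes the two rates. This should be corrected before the tables are run, but it does not undermine the study.

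**What to change.** In SAP 6.9, limit the use of all samples to the rows of the YSI-classified tables (A.7.1, A.7.3, A.8.1). For A.7.2, A.7.4, A.8.2 and every Overall row, and likewise protocol Tables 6B, 6D and 7B, choose one of:

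- the 15-minute pairs that SAP 6.2 already defines; or
- all pairs, each weighted by its sampling interval (5-minute pair 1/3, 15-minute pair 1), with the unweighted n shown.

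The cost is a sentence in the SAP and a filter or weight in the table program. Thinning leaves fewer extreme pairs (880 instead of 2320 expected on Day 1); weighting discards none. Some agreement figures in the low and high sensor rows become slightly less favourable: under the flat mix, agreement within 15 mg/dL at CGM 40–80 falls by about 0.6–4.6 points. Mid-range rows improve. The change removes the sampling artefact only. It does not turn data from induced-challenge visits into predictive values for home use, and the tables should not be presented that way.
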